4. STUDY DESIGN

4.1. Overall Design

This is a Phase 3, multicenter, randomized, placebo-controlled, prospective double-blind study designed to evaluate the efficacy and safety of SC guselkumab in reducing the recurrence of CD in adult patients who have recently undergone a surgical resection for CD. A diagram of the study design is provided in Section 1.2, Schema.

A target of approximately 370 participants will be enrolled from approximately 150 sites. The target population consists of participants with CD who have undergone a recent (\leq 49 days) ileocolonic resection with ileocolonic anastomosis for CD, without evidence of active disease postoperatively. Participants must not have had their qualifying surgery for the purpose of resecting known dysplasia.

Participants will have a baseline CDAI <200 and will be eligible regardless of prior biologic use. Participants who are low risk for recurrent CD (ie, participants whose qualifying surgery was their

CONFIDENTIAL - FOIA Exemptions Apply in U.S.

first in >10 years since their diagnosis of CD and was performed for fibrostenotic stricturing disease involving <10 cm of the intestine) will be excluded. Participants must be able to undergo randomization no later than 49 days after surgery. For a full list of entry criteria, refer to Section 5.1.

Randomization will occur in a 1:1 ratio with participants receiving either:

- **Arm 1 (Guselkumab):** Guselkumab at Week 0 and then at Week 8, then thereafter through the end of the total study period.
- Arm 2 (Placebo): Matched placebo at Week 0 and then thereafter through the end of the total study period.

Randomization will be stratified by clinical remission status at baseline (CDAI \leq 150), region (North America, Western Europe, rest of world) and number of prior surgeries (1 surgery versus \geq 1 surgery, with the qualifying surgery counting as 1 surgery).

A Week 48 video ileocolonoscopy will be performed between Weeks 48 and 51 and participants with endoscopic recurrence confirmed by a central reader will cross over to open-label treatment with guselkumab SC induction. An optional video ileocolonoscopy can be performed at Week 24 and optional cross over may occur at the discretion of the principal investigator if there is only endoscopic recurrence without disease recurrence (defined in Section 9.4.3). If participants meet criteria for disease recurrence after Week 8 they will also cross over to open-label treatment.

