proposed maintenance dose of this study, CCI , is the same as the currently approved regimen for guselkumab for the treatment of moderate-to-severe plaque psoriasis. Since psoriasis is a chronic immune mediated disease requiring long-term therapy to maintain disease control, the 2 pivotal Phase 3 studies (CNTO1959PSO3001 and CNTO1959PSO3002) included long-term extensions through a total of up to 5 years. The analyses of pooled data support the conclusion that guselkumab is well tolerated through 5 years of treatment, and the safety profile remains consistent when compared to Week 48 data, at the approved dose regimen of CCI administered CCI at Weeks 0, 4, and then CCI in adult participants with moderate to severe plaque psoriasis.

When infliximab was previously studied in this patient population in the PREVENT trial, the standard induction dosing of 5 mg/kg at Weeks 0, 2, and 6 was also not utilized. Instead, participants were immediately started on the 5 mg/kg IV q8w established maintenance regimen. While this study did not show significance for clinical recurrence at the Week 76 primary endpoint, it showed clear separation in rates of endoscopic recurrence versus placebo and in the time-to-event analysis for clinical recurrence, with the greatest separation seen in the first 6 months, supporting that it is appropriate to forgo a full induction regimen in this patient population.

In the event a participant experiences confirmed disease recurrence, endoscopic recurrence at Week 48, or, at the investigator's discretion for endoscopic recurrence at the optional Week 24 ileocolonoscopy, they will cross over to receive open-label treatment with guselkumab using the regimen under study for moderately-severely active CD in the ongoing Phase 3 study CNTO1959CRD3004. As these patients will, per protocol, have a CDAI that is ≥220 (or at a minimum is very close, at 201-219) and/or confirmed endoscopic activity, giving induction dosing of CCI for 3 doses is appropriate to treat this level of ongoing inflammatory and disease activity from CD that has recurred such that it is now in the moderately-to-severely active category.

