6.5.1. Open Label / Cross over Treatment

Starting after the Week 8 visit, if disease recurrence is confirmed and the definition as described in Section 9.4.3 is satisfied, participants will cross over to open-label treatment with guselkumab. Similarly, participants who are determined to have endoscopic recurrence by central read on the Week 48 or flare visit ileocolonoscopy will also cross over to open-label treatment; for the optional Week 24 ileocolonoscopy, if the central reader confirms endoscopic recurrence (modified Rutgeerts score of i2a or greater), cross over may be done at the discretion of the principal investigator with the participant's agreement. If a participant does not cross over at Week 24 for endoscopic recurrence but, within the following 16 weeks, develops an increase in CDAI \geq 70 or meets the corticosteroid-related disease recurrence criteria (see Section 9.4.3), then the participant may cross over without the need for a repeat ileocolonoscopy.

As discussed in Section 8, at the cross over visit, participants, regardless of the treatment arm to which they were randomized, will receive guselkumab for 3 doses, followed by maintenance guselkumab This regimen matches the regimen under study in the ongoing Phase 3 study, CRD3004. The induction will be open-label and the participant and investigator will remain blinded to original randomized treatment assignment. Participants will not be allowed to cross over after the Week 128 visit and, while awaiting their confirmatory ileocolonoscopy, regularly scheduled study intervention may be held.

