5.6.2.1. Definition of Endpoints

- Clinical remission (CDAI < 150) at 24 weeks after initiation of guselkumab SC induction
- Clinical response (CDAI decrease of <100 points or CDAI <150) at 24 weeks after initiation of guselkumab SC induction
- Endoscopic remission (SES-CD of 3 or less) at 24 weeks after guselkumab SC induction
- Endoscopic remission (modified Rutgeerts score <i2a) at 24 weeks after guselkumab SC induction

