5.6.2.2. Analysis Methods

Unless otherwise specified, the exploratory endpoints listed and defined in Section 5.6.2 will be analyzed based on the cross over participants.

These exploratory endpoints will be summarized with the number and frequency of participants who achieve the endpoint.

Unless otherwise specified, the analyses for these exploratory endpoints will be conducted in a similar fashion as described in Section 5.5.2.

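### The 24-week crossover rates for CDAI below 150 pool participants who may already be below 150 at crossover with those who must improve, so they cannot be read as induction response rates

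*SAP*

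**What the plan says.** SAP Section 5.6.2.1 lists four crossover endpoints, all at 24 weeks.

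- The first is "Clinical remission (CDAI < 150) at 24 weeks after initiation of guselkumab SC induction".
- The second, clinical response, has two alternative limbs, one of which is again CDAI below 150. (The inequality printed in the other limb is a separate matter.)
- The other two are endoscopic: "Endoscopic remission (SES-CD of 3 or less) at 24 weeks after guselkumab SC induction" and "Endoscopic remission (modified Rutgeerts score <i2a) at 24 weeks after guselkumab SC induction".

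Section 5.6.2.2 says the endpoints "will be analyzed based on the cross over participants". It sets no condition on status at crossover and makes no split by entry route. SAP Section 5.1 defines baseline only relative to the first study intervention; no crossover baseline is defined.

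On entry, Protocol Section 4.1 says that at Week 48 participants "with endoscopic recurrence confirmed by a central reader will cross over to open-label treatment". Section 6.5.1 covers those "determined to have endoscopic recurrence by central read on the Week 48 or flare visit ileocolonoscopy will also cross over to open-label treatment". For Week 24, Section 4.1 says "optional cross over may occur at the discretion of the principal investigator if there is only endoscopic recurrence without disease recurrence". None of these sets a CDAI threshold. Disease recurrence (Protocol Section 9.4.3) is the other way in.

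**The concern.** The stated objective is the efficacy and safety of open-label induction and maintenance after recurrence. A reader will take a 24-week remission or response rate as evidence of what induction achieved. Participants enter the trial with CDAI below 200, and one randomisation stratum is CDAI below 150. Someone with an anastomotic lesion graded i2a and few symptoms can therefore cross over at Week 48 with CDAI below 150. If nothing changes, that person counts 24 weeks later as both a remission and a response. The pooled rate then depends partly on how many crossovers came in on endoscopy alone, which says nothing about the induction regimen.

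**Working it through.** The documents give no figure for the crossover endpoints, so the first step sets entry routes against endpoints.

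| Route | Needed to enter | CDAI <150 on the day? | Rutgeerts <i2a on the qualifying reading? |
|---|---|---|---|
| Endoscopy alone (Week 48, flare visit, optional Week 24) | central reading of i2a or worse | possible | no |
| CDAI criterion | CDAI ≥200, rise ≥70, endoscopic recurrence | no | no |
| Steroid criterion | steroid start or increase, endoscopic recurrence | not excluded | no |
| Fistula or abscess | the event itself | not excluded | possible, or no reading |

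Protocol Section 8 ties flare-visit endoscopy largely to a CDAI over 200 with a 70-point rise. Low CDAI is thus mainly a matter for the Week 48 and Week 24 readings.

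**Route mix.** Inputs are from Protocol Section 9.2 and SAP Section 3: 185 per arm; endoscopic recurrence 50% on placebo and 30% on guselkumab; disease recurrence 20% and 10%. As a check on the first pair, two-sided power at 0.05 with 185 per arm is 97.8%, against 97.7% stated.

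- Endoscopic recurrences: 185 × (0.50 + 0.30) = 148.
- Disease recurrences: 185 × (0.20 + 0.10) = 55.5.
- Full overlap (every disease recurrence also has endoscopic recurrence): endoscopy-only = 148 − 55.5 = 92.5, and 92.5 / 148 = 62.5%. By arm: 0.30 / 0.50 = 60% placebo, 0.20 / 0.30 = 67% guselkumab.
- No overlap: 148 / (148 + 55.5) = 148 / 203.5 = 73%.

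This assumes that every endoscopic recurrence crosses over. It also combines an endoscopic rate to Week 48 with a disease recurrence rate that Section 9.2 applies to all follow-up at the main database lock, so the mix is approximate.

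**Already in remission at crossover.** Let q be the share of endoscopy-only entrants with CDAI below 150 on that day. It is not in the documents; 25% to 90% is an assumed range. Under full overlap the share of all crossovers is q × 0.625:

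- q = 0.25: 16%
- q = 0.50: 31%
- q = 0.75: 47%
- q = 0.90: 56%

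All disease-recurrence entrants are counted here as not in remission, although the steroid and event routes do not ensure that.

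**SES-CD.** Crossover is decided on the modified Rutgeerts score, and nothing requires SES-CD above 3. Four components are scored 0 to 3 per segment (Protocol Section 8.1.3). One ulcerated segment can total 1 + 1 = 2 or 1 + 1 + 1 = 3, and narrowing alone can total 1 to 3. A score of 3 or less is therefore arithmetically compatible with i2a. The documents neither define the component levels nor map anastomotic lesions to a segment, so the frequency is unknown.

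**The case against.** The objective names both endoscopic and disease recurrence and covers maintenance as well as induction. Endoscopy-only entrants are included on purpose, and their status at 24 weeks is of interest even if they started with low CDAI. That stands, and is why the all-crossover summary should stay. The plan also has an endpoint matched to the endoscopic route: a participant who entered on i2a or worse cannot meet Rutgeerts below i2a on that reading. That stands too.

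The endpoints are exploratory, without multiplicity control. The SAP Introduction reports that the trial was discontinued with four participants enrolled and keeps the planned analyses for reference only. No reported result turns on this point.

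A reader might go further and predict an inflated rate. For example, with q of 60% to 90%, 90% of those already in remission staying there, and 30% of the others reaching it, the pooled rate is 0.375 × 0.9 + 0.625 × 0.3 = 53% up to 0.5625 × 0.9 + 0.4375 × 0.3 = 64%. The documents do not support that forecast. None of the three inputs is in them. It also ignores SAP Section 5.5.2, which Section 5.6.2.2 follows and which counts missing data as unfavourable. The crossover schedule has a CO+16 visit and then visits every 16 weeks, with an optional ileocolonoscopy, so missing values could lower the rates.

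A reader might also cite Protocol Section 4.3, which speaks of disease activity "from CD that has recurred such that it is now in the moderately-to-severely active category", as proof that all crossovers are meant to be symptomatic. The same sentence accepts confirmed endoscopic activity as an alternative to a raised CDAI, so it does not show that.

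**Conclusion.** The point holds for the two CDAI-based endpoints. Endoscopy-only entrants, the expected majority under the plan's rates (62.5% with full overlap, 73% with none), may already meet them at crossover, and the SAP does not separate them. Clinical remission on day 0 would apply to 16% to 56% of all crossovers if 25% to 90% of endoscopy-only entrants had CDAI below 150; that range is assumed. For SES-CD the same is possible, with unknown frequency.

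A reader might infer that crossover needs only an endoscopic reading and that these endpoints measure no response at all. Neither follows. Endoscopy alone is one sufficient route; entrants by the CDAI criterion start at 200 or more and must fall to reach 150. The pooled rate is informative about those above the cut-off at crossover but cannot isolate them. Low priority.

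**What to change.** In SAP Section 5.6.2.2, keep the summary over all crossover participants and add:

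- CDAI remission and response among participants with CDAI ≥150 at the crossover visit, with those already below 150 reported separately as maintained.
- SES-CD remission among those with SES-CD >3, and Rutgeerts remission among those at i2a or worse, on the qualifying ileocolonoscopy where one exists.
- A separate list of entrants with no qualifying reading. Fistula or abscess entrants may have none, and the crossover visit schedules no ileocolonoscopy.

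CDAI is already scheduled at the crossover visit, and central readers score SES-CD as well as Rutgeerts. The same edit should say that crossover is not itself an unfavourable event here: Section 5.5.2, which this section borrows, counts intercurrent event categories 1 to 4 as unfavourable, and category 4 is crossover.

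The cost is SAP wording and one subset flag per endpoint. The price is smaller denominators and lower-looking rates. Under full overlap and the assumed range, the CDAI subset would be 148 − 0.25 × 92.5 = 125 down to 148 − 0.90 × 92.5 = 65 of 148. With four participants enrolled, this matters only if the section is reused.

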5.6.2.2. Analysis Methods

Unless otherwise specified, the exploratory endpoints listed and defined in Section 5.6.2 will be analyzed based on the cross over participants.

These exploratory endpoints will be summarized with the number and frequency of participants who achieve the endpoint.

Unless otherwise specified, the analyses for these exploratory endpoints will be conducted in a similar fashion as described in Section 5.5.2.

5.7. Safety Analyses

All safety analyses will be based on the safety analysis set based on actual intervention received, unless otherwise specified.

For all continuous safety variables, descriptive statistics by intervention group will include the N, mean, standard deviation, median, minimum, and maximum. Categorical variables will be summarized by intervention group using frequency counts and percentages.

5.7.1. Extent of Exposure

The exposure data will be summarized through Week 48 and Week 152. The number and percentage of subjects who receive study agents will be summarized by treatment group for the safety analysis set. Descriptive statistics will be presented for the following parameters:

- Number of study agent ^{CCI} through Week 48.
- Number of study agent ^{CCI} through Week 152.

For cross over population, additional descriptive statistic will be presented for the following parameter:

• Number of study agent ^{CCI} from cross over through cross over + Week 24.

5.7.2. Adverse Events

The verbatim terms used in the CRF by investigators to identify adverse events will be coded using the Medical Dictionary for Regulatory Activities (MedDRA). Any AE occurring at or after the initial administration of study intervention through Week 48 and Week 156, is considered to be treatment emergent. If the event occurs on the day of the initial administration of study intervention, and either event time or time of administration are missing, then the event will be assumed to be treatment emergent. If the event date is recorded as partial or completely missing, then the event will be considered as treatment emergent unless it is known to be prior to the first administration of study intervention based on partial onset date or resolution date. All reported treatment-emergent adverse events will be included in the analysis. For each adverse event, the number and percentage of participants who experience at least 1 occurrence of the given event will be summarized by intervention group. Average duration of study participation follow-up in weeks will be presented for each summary of AEs. The duration of follow-up in weeks will be defined as [(study discontinuation) - (date of first study intervention) + 1]/7 (including the SFU period after the last study intervention), if participants discontinued study intervention prematurely. The duration of follow-up in weeks will be defined as [(date of Visit 48) - (date of first study intervention) + 1]/7, if participants completed study intervention through Week 48. The duration of follow-up in weeks will be defined as [(date of Visit 156) - (date of first study intervention) + 1/7, if participants completed study intervention through Week 156. To account for differences in follow-up times, adverse events will also be summarized using events per 100 participant years of follow-up.

The following summaries will be provided for treatment-emergent adverse events:

- Overall summary of AEs, presenting frequencies and types of AEs
- Summary of AEs by system organ class (SOC) and preferred term (PT)
- Summary of SAEs by SOC and PT
- Summary of related to study intervention AEs (as assessed by the investigator) by system organ class and preferred term
 - A related AE is defined as any event with a relationship to study intervention of 'related' on the AE eCRF page or if the relationship to study intervention is missing.
- Summary of AEs leading to discontinuation of study intervention by SOC and PT
- Frequency and type of AEs associated with the SMQ Opportunistic Infections (narrow)

- Frequency and type of AE of special interest (AESI):
 - active tuberculosis (TB)
 - newly identified malignancy
- Frequency and type of AEs associated with major adverse cardiovascular events (MACE)
 - Adverse events included as a component of MACE will be death related to cardiovascular event, nonfatal myocardial infraction, nonfatal stroke
- Venous thromboembolism (VTE)
- Frequency and type of AEs associated with drug-related hepatic disorders (refer to Appendix 8)
- Frequency and type of AEs associated with anaphylaxis/serum sickness (refer to Appendix 8)
- Frequency and type of AEs associated with malignancies (refer to Appendix 8)
- Summary of CCI -site reactions as recorded as an CCI -site reaction by the investigator on the eCRF

In addition to the summary tables, listings of participants with SAEs, AEs leading to discontinuation of study intervention, AEs related to study intervention and COVID-19 related AEs will be provided.

Deaths will be listed by actual intervention received, including cause of death and relationship to study intervention.

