1.2.3. Randomization and Blinding

Randomization will be used to minimize bias in the initial assignment of participants to intervention groups, to increase the likelihood that known and unknown participant attributes (eg, demographic and baseline characteristics) are evenly balanced across intervention groups, and to enhance the validity of statistical comparisons across intervention groups. In addition, stratification by known potentially relevant baseline characteristics that may affect study outcomes will also be used to avoid chance imbalance of these relevant variables among treatment groups. Blinded intervention will be used to reduce potential bias during data collection and evaluation of clinical endpoints.

Intervention Allocation

Procedures for Randomization and Stratification

Central randomization will be implemented in this study. At Week 0, participants will be randomly assigned to 1 of 2 intervention groups in a 1:1 ratio based on a computer-generated randomization schedule prepared before the study by or under the supervision of the sponsor. The randomization will be balanced by using randomly permuted blocks and will be stratified by clinical remission status at baseline (CDAI < 150, CDAI \ge 150), region (North America, Western Europe, rest of world) and number of prior surgeries (1 surgery versus > 1 surgery, with the qualifying surgery counting as 1 surgery). The IWRS will assign a unique intervention code, which will dictate the intervention assignment and matching study intervention kit for the participant.

Blinding

To maintain the study blind, the study intervention container will have a label containing the study name, study intervention number, and reference number. The study intervention number will be entered in the eCRF when the study intervention is dispensed. Each active study intervention and its matching placebo will be identical in appearance and will be packaged in identical containers. All participants will receive the same device(s), which could be either active or matching placebo at 8-week intervals to maintain treatment blinding.

The investigator will not be provided with randomization codes. The codes will be maintained within the IWRS, which has the functionality to allow the investigator to break the blind for an individual participant.

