3. SAMPLE SIZE DETERMINATION

A sample size of 370 participants (185 participants assigned to guselkumab and 185 assigned to placebo) will allow to have at least 90% power to detect 20% differences between guselkumab (30%) and placebo (50%) for endoscopic recurrence rate (primary endpoint) at Week 48, assuming a 2-sided alpha level of 0.05.

This also will allow at least 90% power to detect 17% differences between guselkumab (37%) and placebo (20%) for clinical remission without disease recurrence at Week 48, assuming a 2-sided alpha level of 0.05. This also will allow 90% power to detect 10% differences between guselkumab (10%) and placebo (20%) for disease recurrence at the main database lock, all available follow-up of all participants will be used to examine disease recurrence at the time of the primary database lock.

Endoscopic Recurrence

Assumptions for endoscopic recurrence prior to or at Week 48 were based on previous studies, as described in Table 2.

Reference*	Endoscopic Recurrence definition	Sample Size	Placebo rate	Timepoint
		-		-
Regueiro 2016	Rutgeerts \geq i2	150	60%	76 weeks
Yamamoto 2007	Rutgeerts \geq i2	20	70%	52 weeks
Marteau 2006	Rutgeerts \geq i2	47	64%	24 weeks
Rutgeerts 2005	Rutgeerts \geq i2	33	78.8%	52 weeks
Hanauer 2004	Rutgeerts \geq i2	40	64%	104 weeks
Lochs 2000	Rutgeerts \geq i2	166	50%	72 weeks
Ewe 1999	Rutgeerts \geq i2	40	70%	52 weeks
Hellers 1999	Rutgeerts \geq i2	66	58%	52 weeks

Table 2:	Endoscopic	Recurrence,	Placebo	Group
----------	------------	-------------	---------	-------

* References are provided in the protocol.

Based on these data above, the endoscopic recurrence rates are assumed to be 50% for placebo and 30% for guselkumab.

To accommodate other potential scenarios, power was calculated based on different assumptions as listed in Table 3.

Event rate at Week 48 for endoscopic recurrence in placebo group	Event rate at Week 48 for endoscopic recurrence in guselkumab group	Difference to be detected	Power
50%	30%	20%	97.7%
50%	25%	25%	99.9%
50%	35%	15%	83.3%
45%	25%	20%	98.3%
40%	20%	20%	98.9%
60%	30%	30%	>99.9%

 Table 3:
 Power to Detect a Treatment Effect Based on Different Scenarios in Endoscopic Recurrence

Clinical Remission without Disease Recurrence

Based on data from PREVENT (20% for placebo, and 36.7 for Infliximab), the rates of clinical remission without disease recurrence are assumed to be 20% for placebo and 37% for guselkumab.

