Accrual time used here is 18 months, total time used here is 30 months. It is expected median follow-up time available at the time of, and thus incorporated in, the main database lock is approximately 18 months. Assuming non-uniform accrual pattern: 25% of participants will be enrolled in the first 6 months, 35% of participants will be enrolled in the next 6 months, and 40% will be enrolled in the last 6 months. Assuming dropout rate is 15% annually. Average duration of follow-up is expected to be approximately 20 months.

Analysis Sets	Description
Randomized	The randomized analysis set includes all participants who were
	randomized in the study.
Full Analysis Set (FAS)	All randomized participants.
	Participants in the FAS will be analyzed according to their randomized study intervention regardless of the study intervention they actually received.
Safety Analysis Set	All randomized participants who receive at least 1 dose of study intervention.
	Participants in the Safety Analysis Set will be analyzed according to the study intervention they actually received.
Pharmacokinetics Analysis Set	All randomized participants who receive at least 1 dose of study intervention and have at least one valid blood sample drawn postbaseline for PK analysis.
	Participants in the PK Analysis Set will be analyzed according to the study intervention they actually received.
Immunogenicity Analysis Set	All participants who received at least 1 dose of study intervention and have appropriate samples for anti-drug antibody detection.
	Participants in the Immunogenicity Analysis Set will be analyzed according to the study intervention they actually received.

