4. POPULATIONS (ANALYSIS SETS) FOR ANALYSIS

5. STATISTICAL ANALYSES

5.1. General Considerations

- Unless otherwise specified, for each study, data from all investigational centers/sites will be pooled for analysis
- Study Day 1 refers to the day of the first study intervention administration. All efficacy and safety assessments at all visits will be assigned a day relative to this day.

Study day for a visit is defined as:

- Visit date (date of Study Day 1) +1, if visit date is \geq date of Study Day 1
- Visit date date of Study Day 1, if visit date < date of Study Day 1

There is no 'Study Day 0'.

- Baseline assessment is defined as the last available assessment collected prior to the first study intervention.
- Descriptive statistics (ie, N, mean, median, SD, IQ range, minimum and maximum) will be used to summarize continuous variables. Counts and percentages will be used to summarize categorical variables. Graphical data displays (eg, line plots) may also be used to summarize the data.

CONFIDENTIAL – FOIA Exemptions Apply in U.S.

- The following conventions will be applied for reporting descriptive statistics of all continuous parameters. For presentation, the mean and median will be presented to 1 decimal greater than the original data, SD will be 2 decimal places greater than the original data, and the minimum and maximum will have the same number of decimal places as the original data.
- The following intervention groups will be presented through Week 48, unless otherwise stated:
 - Placebo
 - Guselkumab

Partial dates for adverse events will be imputed as described in Appendix 11.

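### Week 156 AE, laboratory and C-SSRS summaries are not cut at crossover, and the as-treated rule does not place a participant who takes placebo and then open-label guselkumab

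*SAP*

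**What the plan says.** **Window and denominator.** SAP 5.7.2 states: "Any AE occurring at or after the initial administration of study intervention through Week 48 and Week 156, is considered to be treatment emergent". AEs are summarised by intervention group, as participants with at least one event and as events per 100 participant-years. For those who complete treatment to the end, the denominator is given as: "The duration of follow-up in weeks will be defined as [(date of Visit 156) - (date of first study intervention" date, plus one day, divided by 7. Neither the window nor the denominator refers to crossover. SAP 5.7.3.1 (laboratory maxima and shifts) and 5.7.3.2.1 (C-SSRS worst severity) run through Week 48 and through Week 156 in the same way.

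**Grouping.** SAP 5.7: "All safety analyses will be based on the safety analysis set based on actual intervention received, unless otherwise specified". The analysis-set table of SAP Section 4 agrees: "Participants in the Safety Analysis Set will be analyzed according to the study intervention they actually received". Protocol 9.4.5 has the same rule. SAP 5.1 names the columns, Placebo and Guselkumab, under this introduction: "The following intervention groups will be presented through Week 48, unless otherwise stated". No columns are named for later tables.

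**Crossover.** SAP 1.2.1 moves participants in either arm to open-label guselkumab for centrally confirmed endoscopic recurrence at the Week 48-51 ileocolonoscopy, for disease recurrence after Week 8, and optionally after a Week 24 ileocolonoscopy.

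**Where crossover is already handled.** PK is summarised up to crossover and again after it (SAP 5.8.1.1). The time-to-event secondary endpoints have crossover censoring rules (5.4.1.1). One exposure summary runs from crossover to 24 weeks after it (5.7.1). The antibody listing shows crossover status (5.8.2.1).

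**The concern.** An as-treated rule works when each participant receives one treatment, including the wrong one by mistake. Here many participants would receive two in sequence, as the protocol intends. SAP 1.2.3 says that "participants will be randomly assigned to 1 of 2 intervention groups", but a placebo participant who crosses over has received both treatments. Two analysts following the text could therefore put that person in different columns after Week 48, and neither would have broken a written rule.

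What is at stake is the meaning of the Week 156 placebo column. If crossers stay in it, the column mixes placebo and guselkumab exposure, and a real difference shrinks. If crossers leave it altogether, the column holds only people who did not recur. In neither case does any AE, laboratory or C-SSRS summary isolate the open-label period. Yet SAP 1.1 includes safety of open-label treatment in one of its Other objectives, and SAP 5.6.2, the section on crossover analyses, lists efficacy endpoints only.

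**Working it through.** The SAP prints no figure for this point, so the size is an illustration on its planning values.

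**Inputs from the SAP.** 185 per arm; "the endoscopic recurrence rates are assumed to be 50% for placebo and 30% for guselkumab"; "Assuming dropout rate is 15% annually" (all Section 3). Crossover at Weeks 48-51 (1.2.1). Table cut-off T = 156 weeks.

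**Assumptions.** Everyone planned to recur crosses at week t = 48 or 51 and stays on treatment, and no one crosses later. AE rates are constant and equal on blinded and open-label guselkumab. The true guselkumab-to-placebo AE rate ratio R is 1.3 or 2.0.

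**1. Anchor.** The plan's power for 50% v 30% with 185 per arm (two-sided 0.05, pooled variance) recomputes to 97.77%, against 97.7% stated. This confirms only that 50% and 30% are the rates the plan was built on.

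**2. Share of placebo-arm time on guselkumab, no dropout.** s = p(T − t)/T with p = 0.5.
- t = 48: 0.5 × 108/156 = 34.6%
- t = 51: 0.5 × 105/156 = 33.7%

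With 185 × 156/52.18 = 553 participant-years in the arm, that is about 192 and 186 participant-years.

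**3. With dropout.** L = −ln(0.85)/52 per week, and s = p[exp(−Lt) − exp(−156L)]/[1 − exp(−156L)].
- t = 48: 31.9%
- t = 51: 30.9%

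**4. Crossers kept under placebo.** The placebo column's rate becomes (1 − s) + sR times the true placebo rate, so the ratio shown is R/[(1 − s) + sR].

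| Scenario | s | R = 1.3 shown as | R = 2.0 shown as |
|---|---|---|---|
| No dropout | 33.7-34.6% | 1.18 | 1.49-1.50 |
| 15% annual dropout | 30.9-31.9% | 1.19 | 1.52-1.53 |
| Low: 20% cross at Week 48, no dropout | 0.2 × 108/156 = 13.8% | 1.25 | 1.76 |
| High: 60% cross at Week 24, no dropout | 0.6 × 132/156 = 50.8% | 1.13 | 1.33 |

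A true ratio of 1.0 stays at 1.0 under these assumptions.

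**5. Whole crossers moved to guselkumab.** The placebo column falls to 185 × 0.5 = 92.5, about 93 participants, all without recurrence. The guselkumab column rises to 185 + 92.5 = 277.5 and takes in the placebo-period events of people who recurred. Protocol 8.5.4 lists events of worsening Crohn's disease as anticipated. Such events would leave the placebo column because of the outcome, even if the drug had no effect on them.

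**6. Guselkumab column.** About 185 × 0.3 = 55.5 participants would also cross, to a different open-label regimen. Their time after crossover is 0.3 × 108/156 = 20.8% (t = 48) or 0.3 × 105/156 = 20.2% (t = 51) of that arm's time.

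**7. Week 48 tables.** Crossover driven by the Week 48 ileocolonoscopy falls at or after this cut-off. If 10-20% of placebo participants cross at Week 24 (assumed), s = p × 24/48 = 5-10%. Then 1.3 appears as 1.28-1.26 and 2.0 as 1.90-1.82.

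**The case against.** **The SAP plans no safety rate ratio.** It plans counts, percentages and events per 100 participant-years. This is correct: the ratios above are what a reader would form from two adjacent columns, with R assumed. They do not describe the percentage with at least one event, which would need an assumed event probability. The share of placebo-arm time on guselkumab does not depend on R.

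**Crossover is handled elsewhere, and listings exist.** A reader might infer that the SAP overlooks crossover throughout. It does not: PK, the time-to-event endpoints, one exposure summary and the antibody listing all take account of it. None of these yields an AE, laboratory or C-SSRS summary for the open-label period, and the AE listings give no rates.

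**The text might seem to allow many allocations.** A reader might infer that events may go to the treatment at onset, or that open-label guselkumab may have its own column, and that equal true rates would then look very unequal. The documents do not support this. SAP 5.7.2 gives one uncut follow-up time per participant, which fits neither allocation. The SAP Introduction defines study intervention as placebo and guselkumab only. Any figure for such a distortion would rest on a denominator the SAP does not give.

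**Allocation might seem harmless if true rates are equal.** That holds only if crossers stay under placebo. Moving whole crossers selects on recurrence, so it fails there.

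**Open-label safety is a low-ranking aim.** It is an Other objective with only efficacy endpoints beside it. That limits the weight of the gap but does not close it.

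**The study was stopped.** The SAP Introduction reports four participants enrolled and keeps the planned analyses for reference. This stands in full.

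**Conclusion.** The point holds as a minor defect of the plan as designed. The safety window and the follow-up formula to Week 156 are uncut, the as-treated rule does not place a participant who takes placebo and then open-label guselkumab, and no reporting groups are defined after Week 48. On the planning values, about a third of placebo-arm time to Week 156 would be on open-label guselkumab: 34-35%, or 31-32% with planned dropout. Kept under placebo, crossers would pull an assumed ratio of 1.3 to about 1.18 and 2.0 to about 1.5. Moved whole, they would leave about 93 placebo participants selected for no recurrence.

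These sizes rest on everyone planned to recur crossing at Weeks 48-51 and staying on treatment, constant rates, and equal rates on both guselkumab regimens. Later crossover, allowed up to Week 128, would raise the share; early stopping of open-label treatment would lower it. Week 48 tables are affected much less. No conclusion about the drug's actual safety follows, and with four participants no reported result turns on this.

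**What to change.** In SAP 5.7.2 and 5.7.3:

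- For the placebo v guselkumab summaries, stop both event counting and person-time at the first open-label dose. Apply the same cut to laboratory maxima and C-SSRS worst severity.
- Add post-crossover columns by randomised arm (placebo to guselkumab, guselkumab to guselkumab), with events and person-time counted from the first open-label dose.

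In SAP 5.1, define the reporting groups after Week 48.

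The cost is SAP wording and extra table shells; no new data are needed. There are two statistical downsides. Placebo time to Week 156 falls from about 553 to 362-367 participant-years without dropout (553.1 − 191.5 and 553.1 − 186.1). The cut is also informative, because the placebo time left after Week 48 comes mainly from participants without recurrence. For that reason the existing listings through Week 156 should stay, and late events should be shown with both treatments the participant received.
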